6.2.1.7 Hospitalization

Hospitalization will be documented from the time of hospital admission until Day 28 or discharge, whichever occurs earlier. Days and hours in the PICU will be indicated.

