3.5 Assignment of Analysis Sets to Analysis

The FAS serves as the primary efficacy analysis set. All efficacy analyses are based on the FAS. The mFAS and the PP serve as sensitivity populations for the efficacy analyses.

The SAF will be used for the evaluation of the safety assessments.

4 Statistical Evaluation

Continuous variables will be summarized by mean, standard deviation, median, lower and upper quartiles, minimum and maximum. Frequencies and percentages will be used to summarize categorical variables.

Analyses will be performed by visit and treatment group, if not stated otherwise. Baseline will be defined as the most recent non-missing value prior to surgery.

For time to event analyses censoring information will be used for statistical analyses. Handling of missing values is described in detail in the following sections. If no method is described, no imputation of missing values will be applied.

Any parameter describing a “duration” or “length” is calculated as stop date/time - start date/time + 1.

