The same definitions (only using invasive ventilation stop date/time and invasive ventilation breaks: FVS, PVS and other invasive) and analyses as described for the primary endpoint will be applied.

Length of PICU stay

The length of PICU stay will be calculated as the total number of days postoperative until discharge from PICU. The length will be derived as the number of days from day after surgery (variable "Date of surgery" on CRF "Surgery" + 1) until discharge from PICU (variable "Date transferred to floor" on CRF "Post-operative observation"). If subject has to be readmitted to PICU, time will continue to accrue (variables "Date of readmission" and "Date transferred to floor" (second assessment) from CRF "Post-operative observation").

- Length of PICU stay (days) =
(Date transferred to floor - (Date of surgery + 1) + 1) +
(Date transferred to floor (2nd assessment) - Date of readmission + 1)

For subjects who died before discharge from PICU or before Day 28, respectively, the observed length of PICU stay will be used. As sensitivity analyses subjects who died will (1) be excluded from analysis and (2) be assigned a length of PICU stay of 28 days.

For the length of PICU stay the same analyses as described for the primary endpoint will be applied.

Length of time on vasodilators

Length of time on vasodilators will be measured from first use following separation from bypass, until the subject is discharged from the hospital or at Day 28. The length will be derived as the time in minutes from separation from CPB (variable "End time" of parameter "CPB" from section "Post incision" on CRF "Surgery") until last use (last "end date/time" of any medication as documented in sections "Vasodilators" or "Other vasodilators" on CRF "Inotropes and Vasoactive Medications").

- Length of time of vasodilators (min) =
Last "end date/time" of any vasodilators - End time (CPB) + 1

Any interruptions will discontinue to accrue, any duration of re-use of vasodilators will continue to accrue. If a subject did not use any vasodilators the length is set to 0. As a sensitivity analysis, subjects with no use of vasodilators will be excluded. For subjects who died before discharge from the hospital or before Day 28, respectively, the observed length of time on vasodilators will be used. As sensitivity analyses subjects who died will (1) be excluded from analysis and (2) be assigned a length of time on vasodilators of 28 days.

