4.7 Analysis of Other Relevant Variables

Arterial blood gases (ABG)

The number of patients with any low or high values for AGB parameters PaO₂, PaCO₂, HCO₃, pH per 6 hour time window and overall will be evaluated.

6 hour time windows from time of post-op admission to the PICU will be defined as:

- Time of AGB evaluation = Time collected AGB - Time of admission to PICU
- >0 to \leq 6 hrs (>0min to \leq 360min)
- >6 to \leq 12 hrs (>360min to \leq 720min)
- >12 to \leq 18 hrs (>720min to \leq 1080min)
- ...
- >42 to \leq 48 hrs (>2520min to \leq 2880min)
- >48 hrs (>2880min)

Normal ranges for the AGB parameters are defined as:

- PaO₂: <70 mmHg = low; 70-100 mmHg = normal; >100 mmHg = high
- PaCO₂: <35 mmHg = low; 35-45 mmHg = normal; >45 mmHg = high
- HCO₃: <22 mmol/L = low; 22-26 mmol/L = normal; >26 mmol/L = high
- pH: <7.35 = low; 7.35-7.45 = normal; >7.45 = high

Patients will be categorized per AGB parameter and per time window (and overall) as follows:

- Low: At least one value at one visit was low
- Normal: All values at all visit were normal
- High: At least one value at one visit was high
- Low/High: At least one value at one visit was low, and at least one value at one visit was high

The number of patients for those categories will be tabulated per AGB parameter and per time window (and overall).

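### The SAP's PICU-stay formula counts a date twice when a child is transferred out and readmitted on the same day, and it has no term for a second readmission

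*SAP*

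**What the plan says.** SAP 4.4.2 describes the endpoint in words and then as a formula.

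- **Unit.** "The length of PICU stay will be calculated as the total number of days postoperative until discharge from PICU". Protocol 7.1.4 also uses days.
- **Start.** "The length will be derived as the number of days from day after surgery", so the day of surgery is not counted.
- **First-stay term.** "Date transferred to floor - (Date of surgery + 1) + 1".
- **Readmission.** "If subject has to be readmitted to PICU, time will continue to accrue". The formula adds a single term for this, "Date transferred to floor (2nd assessment) - Date of readmission + 1", and ends there.

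The opening of SAP section 4 sets a general rule that any duration or length "is calculated as stop date/time - start date/time + 1". Both PICU terms are written in that shape, using date variables only.

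Two other places refer to finer timing. Protocol 6.2.1.7 states "Days and hours in the PICU will be indicated", and SAP 4.7 sets its blood-gas windows by "Time of AGB evaluation = Time collected AGB - Time of admission to PICU". SAP section 5, which lists changes from the protocol, does not mention the PICU derivation. Protocol 7.1.4 has no readmission rule for this endpoint, although Table 1 in Protocol 6.2.2.1 lists readmission to the unit among the expected events.

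**The concern.** The two terms are added together but treat the entry date differently. In the first term the start is moved forward by one day and the added day cancels. In the readmission term the start is not moved and the added day remains. A same-day return then adds a date that the first term has already counted, so a child who left the unit scores more PICU days than one who never left.

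The formula is also incomplete. A child readmitted twice has a third stay with no term, and the programmer would have to choose a rule after seeing the data structure.

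At stake is the validity of one secondary endpoint. It is not a trivial one. Protocol 1.4 presents the primary composite as a surrogate for time in intensive care, so PICU stay is the direct check on that argument. It receives the same set of analyses as the primary endpoint, on three analysis sets.

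**Working it through.** The documents give no worked example, power or expected value for PICU stay, so there is no stated figure to reproduce. The check is algebra on the SAP formula.

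**Notation.** S = date of surgery (Day 0), T1 = first transfer to the floor, R = readmission, T2 = second transfer to the floor.

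**Step 1: simplify the two terms.**

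- First stay: T1 − (S + 1) + 1 = T1 − S.
- Readmission: T2 − R + 1.
- SAP total: (T1 − S) + (T2 − R + 1).

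**Step 2: score examples under the SAP and under two consistent rules.** Rule A sums date differences, (T1 − S) + (T2 − R). Rule B counts each distinct postoperative date with any PICU presence once.

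| Course | SAP | Rule A | Rule B |
|---|---|---|---|
| Unbroken, out Day 5 | 5 | 5 | 5 |
| Out Day 3, in Day 3, out Day 5 | 3 + 3 = 6 | 3 + 2 = 5 | Days 1–5 = 5 |
| Out Day 3, in Day 4, out Day 5 | 3 + 2 = 5 | 3 + 1 = 4 | Days 1–5 = 5 |
| Out Day 3, in Day 5, out Day 7 | 3 + 3 = 6 | 3 + 2 = 5 | Days 1–3 and 5–7 = 6 |
| Out Day 3, in Day 5, out Day 5 | 3 + 1 = 4 | 3 + 0 = 3 | Days 1–3 and 5 = 4 |

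The SAP agrees with Rule B in every row except the same-day return. It exceeds Rule A by exactly 1 day whenever there is a readmission. The same-day return is the only pattern that is wrong under both rules.

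**Step 3: a second readmission.** Take out Day 3, in Day 4, out Day 5, in Day 6, out Day 8. The formula as written stops at 3 + 2 = 5. Rule A gives 3 + 1 + 2 = 6 and Rule B gives Days 1–8 = 8. The shortfall depends on the length of the third stay.

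**Step 4: size in the arm means.** The over-count is at most 1 day per readmission, so the upward shift in an arm mean is at most the readmission rate × 1 day. The documents give no rate. Assumed rates of 2% to 15% give 0.02 to 0.15 day per arm. The between-arm shift is then:

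- equal rates: 0;
- 5% vs 2%: 0.05 − 0.02 = 0.03 day;
- 10% vs 5%: 0.10 − 0.05 = 0.05 day;
- 15% vs 5%: 0.15 − 0.05 = 0.10 day.

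These are upper limits, reached only if Rule A is the intended measure. If Rule B is intended, only same-day returns contribute.

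**Step 5: does using dates instead of hours lose power?** This was simulated with Wilcoxon tests at two-sided 5%, 92 per arm. The assumptions are lognormal PICU hours with log-SD 0.8, PICU entry between 11:00 and 17:00, drug stays 30% shorter and a placebo median of 24 h. If children can leave at any hour, power is 83% with hours and 76% with dates. If transfers happen only in daytime, it is 63% with hours and 73% with dates. The sign depends on transfer practice, which the documents do not describe, and the size depends on how the daytime slot is modelled.

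**The case against.** The strongest defence is that the two terms do match. The SAP starts the count on the day after surgery and applies its general inclusive rule, so the first term is an inclusive count of postoperative dates from Day 1 to the transfer date. The readmission term is an inclusive count as well. On that reading, out Day 3, in Day 4, out Day 5 means PICU presence on five dates, and a score of 5 is right.

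This stands for every readmission on a later date. It disposes of a stronger reading that a reader might infer, namely that every readmission is over-counted by one day. That holds only against an elapsed-day rule, which the SAP does not state. The defence does not rescue the same-day return, where one date enters both terms, and it does not supply a rule for a third stay.

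A reader might also infer that using dates throws away precision, since Protocol 6.2.1.7 mentions hours and SAP 4.7 uses a PICU admission time. The documents do not support this as a fault. Days are the protocol's own unit for the endpoint. The SAP names only date variables for transfer and readmission, so clock times for those events are not shown to be on the CRF. The power comparison changes sign with the assumed transfer hours.

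Finally, simply deleting the added day has its own cost: a readmission that begins and ends on one date then scores 0. That is a reason to choose and name the convention deliberately.

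**Conclusion.** As written, the formula is wrong for a same-day transfer and readmission (6 days instead of 5 in the example) and silent on a second readmission. Both follow from the SAP text alone and need no assumptions.

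The effect is small. The double count is at most 1 day per readmission, and at assumed readmission rates of 2% to 15% it moves an arm mean by no more than 0.02 to 0.15 day. A missing third stay works the other way and would under-count by the length of that stay, but only in children readmitted twice. SAP 4.4.2 labels all secondary analyses exploratory. The primary endpoint, its test and the sample size are unaffected. Neither a general one-day over-count of readmissions nor a loss of power from using dates is established.

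**What to change.** Apply one day-count rule to all PICU stays and name it in SAP 4.4.2. Either of these works:

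1. **Summed date differences:** (T1 − S) + (T2 − R) + the same difference for each further stay. This deletes the added day in the readmission term. The SAP should then note that it departs from the general duration rule in section 4, and that a readmission beginning and ending on one date scores 0.
2. **Distinct dates:** the number of postoperative calendar dates with any PICU presence, each counted once. This keeps the present scores for readmissions on a later date and removes the double count.

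Extend the chosen rule to every readmission and list it in SAP section 5, where the inotrope derivation is already recorded. If the CRF holds clock times for transfer and readmission, an elapsed-hours version could be added as a sensitivity analysis, without claiming a gain in power.

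The cost is a short SAP edit and a few lines of programming. No new data are needed for either day-count rule, provided the CRF holds dates for any further stays.

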	Each enrolled subject will be randomized to receive either L-citrulline or placebo throughout all administrations in the study. Subjects will receive an L-citrulline bolus of 150 mg/kg or placebo at the initiation of cardiopulmonary bypass, the addition of L-citrulline at a concentration of 200 µmol/L or placebo given as a bolus during cardiopulmonary bypass, an L-citrulline bolus of 20 mg/kg or placebo 30 minutes after decannulation from cardiopulmonary bypass, followed immediately by a 9 mg/kg/hr continuous L-citrulline infusion or placebo for up to 48 hours.
	The study drug or placebo infusion will be discontinued once invasive arterial blood pressure monitoring is discontinued or at 48 hours, whichever comes first. Subjects will be followed until Day 28 or discharge from the hospital, whichever comes first. For subjects discharged prior to Day 28, a final assessment via telephone will be conducted at Day 28.
Number of Subjects	Approximately 450 subjects will be screened, with 190 randomized to either L-citrulline or placebo in a 1:1 ratio.
Study Treatments:	Eligible subjects will be randomized in a 1:1 fashion to either L-citrulline or placebo and receive the following:
	 Bolus of 150 mg/kg at the initiation of cardiopulmonary bypass, but after removal of any crystalloid base;
	 Addition of study medication at a concentration of 200 µmol/L given as a bolus during bypass. This may be administered as a contemporaneous one-time bolus or multiple administrations to compensate for fluids containing L-citrulline that may be removed from the patient during the course of the operation and thus to

	maintain the concentration of 200 μmol/L;
	 Bolus of 20 mg/kg 30 minutes after decannulation from cardiopulmonary bypass;
	 9 mg/kg/hr continuous infusion for up to 48 hours.
Study Duration	The study will consist of an initial screening phase, followed by enrollment of eligible subjects to the treatment phase on Day 0 (Day of Surgery) and will end once study medication is discontinued: at 48 hours or upon removal of the arterial line. Subjects will be followed until Day 28 or discharge from the hospital, whichever comes first. For subjects discharged prior to Day 28, a final assessment via telephone will be conducted at Day 28.
	The study is planned to be conducted over an 11-month enrollment period.

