1.1 Study Design

This is a multicenter Phase III double-blind, randomized, placebo controlled study to evaluate the efficacy and safety of L-citrulline for the prevention of clinical sequelae of acute lung injury induced by cardiopulmonary bypass (CPB) in pediatric subjects undergoing surgery for congenital heart defects. Children undergoing repair of cardiac defects that include a large unrestrictive ventricular septal defect (VSD) or a partial or complete atrioventricular septal defect (AVSD) or an ostium primum atrial septal defect (ASD) will be eligible for enrollment in this study.

190 subjects will be randomized in a 1:1 fashion to either L-citrulline or placebo. Treatment will include:

- 1) An L-citrulline bolus of 150 mg/kg or placebo at the initiation of CPB, but after removal of any crystalloid base;
- 2) The addition of L-citrulline at a concentration of 200 μ mol/L or placebo given as a bolus during bypass. This may be administered as a one-time bolus or multiple administrations to compensate for fluids containing L-citrulline that may be removed from the patient during the course of the operation and thus to maintain the concentration of 200 μ mol/L;
- 3) An L-citrulline bolus of 20 mg/kg or placebo 30 minutes after decannulation from CPB immediately followed by a 9 mg/kg/hr continuous infusion of L-citrulline or placebo for 48 hours.

The study drug or placebo infusion will be discontinued once invasive arterial blood pressure monitoring is discontinued or at 48 hours, whichever comes first. Subjects will be followed until discharge from the hospital, and a final assessment via telephone will be conducted at Day 28.

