Survival analyses using Kaplan-Meier estimates and plots, log-rank test (significance level of 5%) and Cox-regression modeling including factor treatment (no further factors to be included) will serve as sensitivity analyses. For subjects who died before discharge from the hospital or before Day 28, respectively, the observed length of time on mechanical ventilation/inotropes will be used. The sensitivity analyses (1) and (2) as described for the primary analysis (subjects who died will (1) be excluded from analysis and (2) be assigned a length of time on inotropes of 28 days) will not be applied for survival analyses. The sensitivity analyses (3) and (4) as described for the primary analysis (composite endpoint will be derived with (3) length of time of inotrope use starting on first "start date/time" of inotrope use and (4) length of time of inotrope starting on first "start date/time" of inotrope use and length of time on mechanical ventilation starting on "start date/time" of mechanical ventilation) will be applied for survival analyses. For survival analyses different sets of analyses will be done:

(1) The composite variable for subjects without any mechanical ventilation and without any use of inotropes is set to 0, observations will not be censored

(2) The composite variable for subjects without any mechanical ventilation and without any use of inotropes is set to 0, observations will be censored

(3) Subjects without any mechanical ventilation and without any use of inotropes will be deleted from analysis

For sensitivity analyses (3) and (4) the first set of analyses (i.e., (1) The composite variable for subjects without any mechanical ventilation and without any use of inotropes is set to 0, observations will not be censored) will be used.

Subjects who receive mechanical ventilation or are still using inotropes on the last day of observation (which can be Day 28, Day of early discontinuation, or Day of death) will be censored for survival analyses.

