For the length of time on vasodilators the same analyses as described for the primary endpoint will be applied.

Length of hospitalization

The length of hospitalization will be calculated as the total number of days postoperative until discharge from the hospital. The length will be derived as the number of days from day after surgery (variable "Date of surgery" on CRF "Surgery" + 1) until discharge from the hospital (variable "Hospital Discharge date" on CRF "End of study").

- Length of hospitalization (days) =
Hospital Discharge date - (Date of surgery + 1) + 1

For subjects who died before discharge from the hospital or before Day 28, respectively, the observed length of hospitalization will be used. As sensitivity analyses subjects who died will (1) be excluded from analysis and (2) be assigned a length of hospitalization of 28 days.

For the length of hospitalization, the same analyses as described for the primary endpoint will be applied.

Thoracotomy output - duration and volume of chest tube drainage

The total postoperative duration (in minutes) that the chest tube will be used will be calculated as the time from the end of the surgery (variables "Date of surgery" and "End time" from section/CRF "Surgery") to the time the chest tube will be removed (variable "Date/time of removal" from section/CRF "Thoracotomy Output").

If an additional chest tube is required or reinserted (until discharge from the hospital or at Day 28) the duration that the additional chest tube was used (from time of insertion to time of removal) will be added to the time the original chest tube was used for the total postoperative duration.

- Length of chest tube drainage (min) =
(Time removal - End time (surgery) + 1) +
(Time removal (second assessment) - Time reinsertion + 1)

If a subject did not use any chest tube the duration is set to 0. As a sensitivity analysis, subjects with no use of chest tube will be excluded. For subjects who died before discharge from the hospital or before Day 28, respectively, the observed duration of chest tube drainage will be used.

For the total postoperative duration, the same analyses as described for the primary endpoint will be applied.

Again, as sensitivity analyses subjects who died will (1) be excluded from analysis and (2) be assigned a length of time of chest tube placement of 28 days.

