4.8 Missing Values

Efficacy endpoints describing length of time

If a subject did not receive any mechanical ventilation / inotropes / positive pressure ventilation / intubation / vasodilators / chest tube, the corresponding length of time is set to 0. For subjects who died before discharge from the hospital or before Day 28, respectively, the observed length of time will be used for analysis of all time variables.

For time to event analyses censoring information will be used for statistical analyses.

No other imputation of missing values will be used.

Efficacy endpoint inotrope score

The total inotrope score will be set to zero after the bypass pump has been removed. It will also be set to zero for patients not using inotropes at all.

Further secondary efficacy endpoints

No imputation of missing values will be applied for the secondary endpoints hemodynamic improvement, volume of chest tube drainage, and L-citrulline plasma levels.

Safety endpoints

For laboratory data, concentrations below the limit of quantification will be set to zero. Missing safety data or safety assessments will not be estimated nor imputed. All safety summaries and analyses will be based on observed data.

No other imputation of missing values will be used.

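### Hospital and PICU stay have no Day 28 end rule, so as written a living child still there at Day 28 has no value and drops out of the Wilcoxon comparison.

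*SAP*

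**What the plan says.** **Formulas.** SAP 4.4.2 gives hospital stay in days as "Hospital Discharge date - (Date of surgery + 1) + 1", using the discharge date from the end-of-study CRF page. The first PICU episode is "Date transferred to floor - (Date of surgery + 1) + 1"; a readmission adds a second episode that ends at a second transfer date. Protocol 7.1.4 also defines both stays up to discharge, with no Day 28 end.

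**Collection window.** Protocol 6.2.1.7: "Hospitalization will be documented from the time of hospital admission until Day 28 or discharge, whichever occurs earlier". The protocol synopsis agrees: "Subjects will be followed until Day 28 or discharge from the hospital, whichever comes first". Protocol 5.1.2.7 provides a Day 28 visit for children who are still inpatients, so such children are expected. SAP 1.1 reads differently, as does protocol 4.1: "Subjects will be followed until discharge from the hospital, and a final assessment via telephone will be conducted at Day 28".

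**Incomplete stays.** SAP 4.4.2 has a rule for deaths only: the observed length, with exclusion (1) or 28 days (2) as sensitivity analyses. For length-of-time endpoints, SAP 4.8 adds zero for never-users and censoring in time-to-event analyses, and then says "No other imputation of missing values will be used".

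**Analysis.** Both stays take the primary endpoint's methods: Wilcoxon test, Hodges-Lehmann interval, and Kaplan-Meier, log-rank and Cox as sensitivity analyses. The censoring sentence in SAP 4.4.1 covers "Subjects who receive mechanical ventilation or are still using inotropes on the last day of observation" and does not name PICU or hospital stay. SAP 4.4.2 sets a two-sided 5% level and calls all secondary analyses exploratory.

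**The concern.** Whether a child has a value depends on the outcome itself: the longest living stays are the ones left blank. If one arm has more prolonged stays, removing them removes that part of the difference, whether it is benefit or harm.

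It looks like an omission. The text for ventilation, inotropes and vasodilators says each is measured to discharge or Day 28; the text for the two stays does not. The authors did think about stays without a discharge, but only for deaths.

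Length of hospitalization is a stated secondary objective. PICU stay is a secondary endpoint, and protocol 1.4 presents the composite as a surrogate for it.

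**Working it through.** **1. The plan's own figure.** The only sample-size figure is 92 per group for the primary composite (SAP 1.3: effect size 0.600, two-sided 1%, 90% power). Noether's formula gives p = Φ(0.6/√2) = 0.6643. Total N = (2.576 + 1.282)² / [12 × 0.25 × (0.6643 − 0.5)²] = 183.7, or 92 per group. It reproduces and does not involve the stay endpoints.

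**2. The formula on example records (surgery = Day 0).**
- Discharged Day 6: 6 − (0 + 1) + 1 = 6 days.
- Alive and in hospital at Day 28, collection ended: no discharge date, so no value.
- The same child with the stay ended at Day 28: 28 − (0 + 1) + 1 = 28 days.
- Discharged Day 29, if that date is collected: 29 − (0 + 1) + 1 = 29 days. This exceeds the 28 days given to deaths in sensitivity analysis (2), so a death would no longer rank as the longest stay.

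**3. Illustrative size.** The documents give neither the share still inpatient at Day 28 nor a distribution of stay. All inputs here are assumptions. The test is Wilcoxon, two-sided 5%.

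*Set A:* 92 per arm; lognormal stay, median 5.3 (active) versus 6 days (placebo), log-SD 0.45; a share still inpatient at Day 28 added on top.

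| Still inpatient, active / placebo | Power, scored 28 | Power, dropped |
|---|---|---|
| 1% / 2% | 46–47% | 43–44% |
| 2% / 6% | 55–56% | 43% |
| 2% / 10% | 73% | 43% |
| 5% / 5% | no loss from dropping | |

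Ranges are from repeated runs. At 2% / 6% the mean difference moves from −1.6 to −0.8 days. The planned estimator, the Hodges-Lehmann shift, moves less: from −0.85 to −0.66 days.

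*Set B:* 95 per arm; the tail comes from the lognormal itself; kept children are tied at the top rank.

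| Medians, active / placebo (log-SD) | Past Day 28, active / placebo | Power, kept | Power, dropped | Loss |
|---|---|---|---|---|
| 4.5 / 6 (0.7) | 0.4% / 1.4% | 80% | 77% | 3 points |
| 4.5 / 6 (0.9) | 2.1% / 4.3% | 56% | 50% | 6 points |
| 6 / 8 (0.9) | 4.4% / 8.2% | 56% | 44% | 12 points |
| 5.6 / 8 (1.0) | 5.4% / 10.6% | 66% | 51% | 15 points |

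If the arms differ only in the tail (2% versus 10%), rejection is 16% when kept and 5% when dropped. With 2% in both arms it is about 5% either way, so type I error is not inflated.

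**The case against.** **Follow-up may run to discharge.** SAP 1.1 and protocol 4.1 can be read that way. Later discharge dates would then exist and no child would drop out. This stands as a conflict with the synopsis and protocol 6.2.1.7, but it exchanges one problem for another: values above 28 sit beside deaths set to 28.

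**The survival analyses.** A reader might infer that they fail too, because the censoring sentence names only ventilation and inotropes. The documents do not support that. Protocol 7.1.2 applies censoring to all time variables, and SAP 4.8 uses it for time-to-event analyses. Censoring an ongoing stay is the natural reading; it only needs stating.

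**Children sent home straight from PICU.** One might infer that they have no transfer date. That depends on CRF completion rules that are not shown.

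**Hidden harm.** This is also too strong. SAP 4.1 tabulates discharge before Day 28, by treatment group under the default in SAP section 4. Prolonged hospitalization is a seriousness criterion in protocol 6.2.2.1, and serious events are analysed separately.

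**The contrast with the other lengths.** Their formulas also need a recorded stop time; only their text mentions Day 28. And if stay is documented to Day 28, counting 28 observed days is truncation rather than imputation. Both points are fair and make the fix easier, but the written stay formulas still do not do it.

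**Size.** Set A's lognormal alone puts only 0.01% and 0.03% of children past Day 28, so its tails are pure assumption. Eligibility excludes preoperative ventilation or intravenous inotropes, and single-ventricle defects are excluded, which may keep the true tail small.

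**Conclusion.** On the written rules, a living child still in hospital or PICU at Day 28 has no value and is left out of the Wilcoxon test and Hodges-Lehmann interval. The SAP does not state this exclusion. It follows from the formulas, the Day 28 end of documentation and the no-imputation rule. The effect is bias toward no difference when the arms differ in prolonged stays.

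The size is unknown. Under the assumptions above, power falls by a few points at about 1% versus 2% still inpatient and by about 12 points at 2% versus 6%, and does not fall when the tails are equal. The larger losses need tails that the documents give no reason to expect.

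The consequence is limited to two exploratory secondary endpoints. The conflicting follow-up statements must be reconciled in either case. The rule is still worth writing down, because the gap selects on the outcome and costs little to close.

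**What to change.** In SAP 4.4.2:

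- End both stays at the earlier of discharge and Day 28. For PICU, count any discharge from PICU, whether to the floor or home.
- Score a living child still there at Day 28 as 28 days in the Wilcoxon and Hodges-Lehmann analyses. For a child readmitted to PICU and still there at Day 28, say how the open second episode is counted.
- Keep the observed-length rule and both sensitivity analyses for deaths.
- In the Kaplan-Meier, log-rank and Cox analyses, censor a stay still ongoing on the last day of observation (Day 28, early discontinuation or death), whatever the ventilation or inotrope status.
- Report the number still in hospital and still in PICU at Day 28, by arm.

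Reconcile SAP 1.1 and protocol 4.1 with the protocol synopsis and 6.2.1.7 on when follow-up ends.

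The cost is a few SAP sentences and one table row per endpoint, set before unblinding. No new data are needed, since protocol 6.2.1.7 already documents hospital and PICU time to Day 28.
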